#### **9.4. Type and Duration of the Follow-up of Subjects After an Adverse Event**

##### **9.4.1. Follow-Up of Non-Serious AEs**

All non-serious adverse events of severe intensity and possibly or probably related to the investigational product should be followed until the subject has recovered and all concerns have been resolved.

Cases of chronic conditions:

No follow-up is required until the “recovered” status is reached. Once the subject has completed the trial, these cases may be closed with a result category of “recovering” or “not recovered”.

All other non-serious AEs must be followed until the outcome of the event is “recovering” (for chronic conditions) or “recovered”, or until the end of the post-treatment follow-up period set out in the protocol, whichever comes first, and until all concerns related to the AEs have been resolved.

[name]  
Traductor-Intérprete Jurado de INGLÉS  
Nº 9971

#### 9.4.2. Follow-Up of Serious AEs

All adverse events classified as serious (SAEs) must be followed until the outcome of the event is “recovered”, “recovered with sequelae”, or “death”, and until all concerns have been resolved.

The investigator must send the SAE follow-up information to Inmunotek, S.L., as the trial sponsor, within 5 days of obtaining the follow-up information.

### **10. STATISTICS**

#### **10.1. Description of the Statistical Methods to be Used, Including the Schedule of any Planned Interim Analysis**

The study analysis will be performed after the database lock. The intention-to-treat (ITT) population will be composed of subjects who took at least one dose of the trial medication. The analysis will be performed on both the ITT and per-protocol populations.

The randomization will be evaluated by comparing the baseline variables (month 0) in both study groups according to the Consolidated Standards of Reporting Trials (CONSORT) due to their clinical relevance. Qualitative variables will be reported together with their frequency distribution, and quantitative variables will be reported together with their mean and standard deviation, or, in case of asymmetry, with their median and interquartile range. If confounding is detected, the effects will be adjusted with the potentially confounding variables using the appropriate model adjustments.

The following variables will be analyzed to determine whether they follow a normal distribution: number of exacerbations, duration of the episodes, need for antibiotic therapy, number of hospital admissions, duration of the hospital admissions, immunological outcomes described in the trial design (page 67), quality of life, and direct costs.

These variables will be described together with their mean and standard deviation, or, in case of asymmetry, with their median and interquartile range. Differences between the means will be analyzed using Student's T test in the case of variables with a normal distribution and Mood's median test in the case of variables without a normal distribution. The absolute effect (difference in estimators) and its precision will be estimated with a 95% confidence interval (CI) in all cases.

The rate of exacerbations per patient and the severity of these exacerbations will be compared using the chi-square test or Fisher's exact test. The relative risks will be estimated together with their 95% CI. The number needed to treat (NNT) or number of events prevented per treatment will be estimated.

The rate of episodes occurred over time will be calculated, and the hazards ratio (HR) will be estimated together with its 95% CI following a Cox proportional-hazards model. The NNT (number of patients that need to be treated to avoid an event) will also be estimated.

To compare the change in the immunological variables described in the trial design (page 67) at 0, 3, 6, 12, and 18 months, an analysis of covariance will be performed, estimating the mean difference over time in both study groups.

The cost-benefit ratios in the study groups will be estimated together with their 95% CI, and compared using non-parametric tests.

The safety variables will be compared using the chi-square test in the case of qualitative variables or Student's T test in the case of quantitative variables whenever they meet parametric assumptions, or using non-parametric test in the opposite case.

The statistical software that will be used is STATA 11.

---

**10.2. Number of Anticipated Subjects and Rationale. Calculation Method Used for Determining the Sample Size and Data Used for Such Purpose**

The calculation of the sample size is based on the efficacy measured based on the decrease in the number of episodes of COPD exacerbations during the 12-month treatment period of the trial per subject.

The ratio of subjects to be distributed among the active treatment and placebo groups will be 1:1.

We estimate that subjects from group I (active treatment with the bacterial vaccine) will achieve a 60% decrease in their number of COPD exacerbations compared with a 30% decrease among those of group II (placebo). With an alpha error of 0.05 and a beta error of 0.2, and assuming a dropout rate of 20-25%, the number of subjects to be recruited would be 90 per study group, with an overall total of 180 trial subjects.

**10.3. Significance Level to be Used**

The significance level for the efficacy assessment will be 0.05 for a type I error ( $\alpha$ ) and 0.2 for a type II error ( $\beta$ ).

**10.4. Trial Termination Criteria**

The trial shall be considered completed when the last recruited subject completes the last trial visit.

**10.5. Procedures to Justify Missing, Unusual, or False Data**

Prior to the inclusion of the first patient in the trial, the trial monitor will carry out an initiation visit to the site. During this visit, trial investigators will receive training on Good Clinical Practice standards, procedures specific to the trial protocol, and the proper and correct completion of the CRF.

The first trial monitoring visit is planned to take place as soon as the first patient has been included in the trial. The monitor assigned by Inmunotek, S.L. will regularly visit the site during the course of the clinical trial. Each and every one of the trial CRFs are expected to be monitored in order to prevent data loss, identify unusual data, and detect the presence of false data.

In the event of missing data, these will be corrected during the database lock with the last observation carried forward (LOCF) technique, which involves carrying over the last available data to maintain the ITT.

#### **10.6. Procedures for Reporting any Deviation from the Original Statistical Plan**

The regulations in force will be followed when reporting information on any deviation from the original statistical plan.

The final report shall include a description of the deviations from the statistical plan that occurred during the course of the trial.

#### **10.7. Selection of Subjects to be Included in the Analysis**

**Recruited subjects:** subjects signing the informed consent, meeting the selection criteria, and assigned a treatment number.

**Safety analysis population:** randomized subjects who have taken at least one dose.

**Per-protocol efficacy analysis population:** randomized subjects completing the 50-week efficacy assessment period and adequately complying with the protocol. These subjects will be assigned to the actual treatment group.

Any significant deviation from the treatment schedule will result in an exclusion from the “per-protocol” dataset. More detailed information can be found in the Statistical Analysis Plan (SAP).

**Intention-to-treat analysis population:** all randomized subjects who have taken at least one dose and have been subjected to the week 25 assessment. These subjects will be assigned to the corresponding treatment group.

The medical history and demographic data will be described in the intention-to-treat population per treatment group.

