### 6.3.2. Type of Data that will be Collected from the Withdrawn Subjects

All subjects who abandon the trial, regardless the cause, will be included in the statistical evaluation of the trial results, and the total number of withdrawals, the different causes of such withdrawals, and the moment they occurred in relation to the trial period must be recorded in detail.

No data will be collected for the statistical analysis from subjects considered to be screening failures.

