HGUGM	Hospital General Universitario Gregorio Marañón
HCSC	Hospital Clínico San Carlos
CRF	Case Report Form
CAT	COPD ASSESSMENT TEST
ELISA	Enzyme Linked ImmunoSorbent Assay
GCP	Good Clinical Practice
IgAs	Secretory Immunoglobulin A
IMP	Investigational Medical Product
ITT	Intention To Treat Set or Population
LNs	Local/regional mucosa-draining lymph Nodes
MALT	Mucosa-Associated Lymphoid Tissue
NKs	Natural Killer cells
PHA	Phytohemagglutinin
PIDs	Primary ImmunoDeficiencies
PP	Per Protocol Set or Population
RRTIs	Recurrent Respiratory Tract Infections
SAE	Serious Adverse Event
SAP	Statistical Analysis Plan
SUSARs	Suspected Unexpected Serious Adverse Reactions

1. *Revisions*

2. *Introduction*

2.1. *Preface*

This statistical analysis plan (SAP) describes all planned analyses for the Clinical Study Report (CSR) of study MV130-SLG-001, a prospective, randomized, double-blind, parallel, placebo-controlled clinical trial evaluating the safety, clinical efficacy, and immunomodulatory response of a polyvalent bacterial vaccine (Bactek[®]) administered via the sublingual mucosa in subjects with chronic obstructive pulmonary disease (COPD).

The content of this SAP is based on protocol MV130-SLG-001 Amendment version 8. All decisions regarding final analysis, as defined in the SAP document, have been made prior to database lock of the study data.

Other endpoints, including immunological substudies, as well as other potential future analyses of data arising from this trial, will be the subject of future analysis plans.

2.2. *Scope of the analyses*

These analyses will assess the efficacy and safety of MV130 in comparison with placebo and will be included in the clinical study report. This statistical analysis plan (SAP) will give more detailed descriptions of the endpoints in the study and the corresponding analyses.

3. Trial Objectives

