5.1. Population description

Three analysis sets are defined, the Full Analysis Set (FAS), the Per Protocol Analysis Set (PP) and the safety analysis set.

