5.1.2. Intention to Treat Set or Full Analysis Set (FAS)

All randomized subjects who have taken at least one dose. These subjects will be assigned to the corresponding treatment group.

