7.1.2. Handling of Missing Data

No imputation of data will be carried out in case of missing data, but all available data will be used to its full extent.

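### The documents give conflicting ITT definitions and missing-data rules, and the SAP names no primary efficacy set

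*Protocol*

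**What the plan says.** **Who is in the ITT set.** Protocol 10.1 states: "The intention-to-treat (ITT) population will be composed of subjects who took at least one dose of the trial medication". Protocol 10.7 narrows this to "all randomized subjects who have taken at least one dose and have been subjected to the week 25 assessment". Protocol 6.3.2 points the other way: "All subjects who abandon the trial, regardless the cause, will be included in the statistical evaluation of the trial results". SAP 5.1.2 treats the ITT set and the full analysis set (FAS) as one set: "All randomized subjects who have taken at least one dose".

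**Missing data.** Under protocol 10.5, "these will be corrected during the database lock with the last observation carried forward (LOCF) technique", with the stated aim of preserving the ITT set. SAP 7.1.2 says: "No imputation of data will be carried out in case of missing data". Protocol 10.1 does not mention missing data.

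**Which set decides.** SAP 5.1 says: "Three analysis sets are defined, the Full Analysis Set (FAS), the Per Protocol Analysis Set (PP) and the safety analysis set". SAP 7.4 applies the efficacy analyses to all of them and ranks none. Protocol 10.1 names both the ITT and per-protocol (PP) sets, also unranked. SAP 8 describes an FAS analysis of everyone enrolled and calls it secondary.

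**How the two documents relate.** SAP 2.1 says: "The content of this SAP is based on protocol MV130-SLG-001 Amendment version 8". It adds that the decisions on the final analysis were taken before database lock. SAP 8 covers deviations from the protocol and mentions neither the week-25 condition nor LOCF.

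**The concern.** A set that requires attendance at week 25 depends on something that happens after randomisation and may differ between arms. It is not an intention-to-treat set, whatever its label. Two other protocol rules add weight. Voluntary leavers are not followed (6.3.4), and some who withdraw before the six-month assessment are replaced (6.3.3). Early leavers could therefore disappear from the analysis and have others in their place.

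The second problem is the missing hierarchy. The SAP plans efficacy results on the FAS and on PP, where PP means 50-week completers who complied. If the two disagree, nothing written in advance says which one answers the primary objective. SAP 8 adds doubt by attaching the word secondary to the set that would normally be primary. Protocol 10.6 requires the final report to describe deviations from the statistical plan. That discloses a choice afterwards; it does not fix the choice beforehand.

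**Working it through.** **1. ITT definitions compared.**

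| Source | One dose needed | Week-25 assessment needed |
|---|---|---|
| Protocol 10.1 | yes | no |
| Protocol 10.7 | yes | yes |
| SAP 5.1.2 | yes | no |

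Protocol 6.3.2 keeps all who leave. A subject who is dosed and leaves at week 10 is therefore in the ITT set under 10.1, 6.3.2 and SAP 5.1.2, and out under 10.7. The texts cannot all apply. Undosed leavers are screening failures under protocol 6.3.1, so enrolled and dosed subjects should differ little.

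**2. Set sizes.** Inputs from the documents are 180 subjects (2 x 90), dropout d of 20-25%, 52 weeks of treatment, and 18 months in all (78 weeks). The assumptions are that everyone is dosed, exits are spread evenly over T weeks, and nobody is replaced. The planned total of 180 is only a starting size here; its derivation is a separate matter.

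Lost by week 25 = 180 x d x 25/T:
- T = 52: 180 x 0.20 x 25/52 = 17.3 and 180 x 0.25 x 25/52 = 21.6, leaving 162.7 and 158.4.
- T = 78: 11.5 and 14.4, leaving 168.5 and 165.6.

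Fifty-week completers = 180 x (1 - d x 50/T):
- T = 52: 145.4 and 136.7.
- T = 78: 156.9 and 151.2.

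The PP set also requires compliance, so the completer figures are upper limits. The three sets hold 180, about 158-169, and at most about 137-157.

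**3. Replacement.** Suppose every pre-week-25 leaver (T = 52) were replaced once. The at-least-one-dose set becomes 180 + 17.3 = 197.3 to 180 + 21.6 = 201.6. The week-25 set becomes 162.7 + 17.3 x (1 - 0.096) = 178.3, or 158.4 + 21.6 x (1 - 0.120) = 177.4. This is an upper case, because protocol 6.3.3 replaces only withdrawals unrelated to the trial.

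**4. Cost of an unranked pair.** The simulation had no true effect, 90 per arm, equal random dropout of 20% or 25% spread over 12 months, PP as 50-week completers, and 3000 trials per combination. Assumed annual rates were 1.5, 2.1 and 3.0, with dispersion 0, 0.5 and 1.0; the documents give neither. False positives at the 5% level:
- FAS alone, robust Poisson with exposure time: 4.7-6.3%.
- Either FAS or PP significant, same model: 6.0-8.3%.
- Either FAS or PP significant, Mann-Whitney on per-patient rates: 6.8-8.7%.

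The simulation error near 5% is about sqrt(0.05 x 0.95/3000) = 0.4 percentage points.

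**5. LOCF.** If a subject leaves with c exacerbations, carrying the running count forward gives c at month 12. The unimputed raw count is also c, so the two rules agree. They part only if the count is divided by follow-up time, or if LOCF repeats the last interval's count in each later interval. To illustrate, take a constant event rate and leavers observed for half of the 12 months on average. The running count then understates an arm's mean by d x 0.5, which is 10% to 12.5%. With equal dropout both arms shrink alike and their ratio is unchanged.

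**The case against.** The best defence is that the SAP has already settled most of this. Its FAS has no week-25 condition, it imputes nothing, and the week-25 set is not among its three sets. An analyst who follows the SAP alone would not produce that set. Because efficacy is planned on all sets, the FAS and PP results should both be visible. The SAP 8 sentence can be read as an extra all-enrolled sensitivity analysis, and SAP 8 also says that deviations will be listed. Much of this stands. The conflict that is live within the SAP is FAS against PP; the week-25 rule matters because the protocol text still carries it. But seeing both results does not say which one decides, and the promise to list deviations may refer to trial conduct only.

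A reader might infer that the SAP dropped the two rules without explanation. The documents do not establish that. No text follows the SAP's Revisions heading in the supplied copy, and the version of the supplied protocol cannot be confirmed. The two documents also differ elsewhere: 180 against 198 screened (protocol 6, SAP 5.2), and a Madrid residence criterion that only the protocol has. A version mismatch, or an explanation in unseen text, remains possible. The contradiction between protocol 10.7 and protocol 10.1 does not depend on this.

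A reader might also infer that LOCF contradicts protocol 10.1. It does not, because 10.1 is silent on missing data; the conflict is with SAP 7.1.2.

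**Conclusion.** The point holds, as something that should be corrected. Protocol 10.7 contradicts protocol 10.1, protocol 6.3.2 and SAP 5.1.2. Protocol 10.5 contradicts SAP 7.1.2. No document makes one efficacy set decisive.

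The size is moderate. Under even dropout without replacement, the week-25 rule would remove about 12-22 of 180 subjects. Leaving FAS and PP unranked costs about one to three percentage points of false positives, and only if the more favourable result could be chosen. Both figures rest on assumed exit times, and the second also on assumed event rates and dispersion.

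Two further inferences go beyond the documents. One is that the week-25 rule or LOCF favours the vaccine: the documents say nothing about which arm loses more subjects or how leavers' event rates compare, so the direction is not determined. The other is that the primary rank test is seriously distorted by unequal follow-up. That is a separate question. With an assumed 20% against 25% dropout, a Mann-Whitney test on raw counts gave 5.1-6.0% false positives, close to nominal.

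**What to change.** 1. In SAP 7.4, name as the primary efficacy set all randomised subjects with at least one dose, analysed as randomised and including any who were later replaced. State that the PP analysis is supportive.
2. In SAP 8, delete or correct the sentence that calls the FAS analysis secondary, or label it as an additional all-enrolled sensitivity analysis.
3. Withdraw the week-25 condition (protocol 10.7) and LOCF for exacerbation counts (protocol 10.5), or record both in SAP 8 as departures from the protocol. If unseen text already explains them, a cross-reference is enough.

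The cost is a few sentences and no new data. Recruitment was due to end on 31 March 2018 and the SAP lists 2022 software, so a protocol edit would be retrospective; recording the departures in the SAP is sufficient. The wording should be settled before database lock. The documents do not show whether lock has happened, and if it has, the change should be dated and described as made afterwards. The primary test does not change. One limit remains: voluntary leavers are not followed (protocol 6.3.4), so their later exacerbations stay unobserved whichever set is primary.

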## **11. DIRECT ACCESS TO THE SOURCE DATA/DOCUMENTS**

Source documents are defined as all original documents, data, and records (e.g., medical records, clinical and administrative charts, laboratory reports, subject diaries or assessment questionnaires, pharmacy dispensing records, data recorded by computerized tools, copies or transcriptions certified after being verified as exact copies, x-rays, subject files, and records stored at the pharmacy, laboratories, and the medico-technical departments involved in the clinical trial).

Both the principal investigator and the associate investigators will allow the trial monitors to inspect the source documents and case report forms when requested throughout the course of the trial.

The investigator must also enable access to the source data/documents in the following cases:

- In the event that Inmunotek wishes to perform an audit of the Clinical Trial.

- In the event that the Competent Authorities wish to perform a Clinical Trial Inspection as part of the process of confirming the validity of the trial conduct and the integrity of the collected data.
- In the event that the CRECs involved wish to check the Trial's progress.

During the process of obtaining the subject's informed consent, the principal investigator or associate investigators will request the subject's consent in writing to have direct access to their data. The subject's acceptance to participate in the trial also grants their permission to examine, analyze, verify, and reproduce any records and medical reports that may be relevant for the trial's assessment. Any party (e.g., national and international Regulatory Authorities, trial monitors, and auditors) granted direct access to this information must take all reasonable precautions within the limits of the applicable legal requirements to maintain the confidentiality of the subjects' identities and of the information patented by the sponsor.

## **12. QUALITY CONTROL AND ASSURANCE**

Inmunotek, as the trial sponsor, is responsible for implementing and maintaining the trial's quality assurance and control systems through updated Standard Operating Procedures and the correct monitoring of the Clinical Trial.

To ensure the trial's quality, Inmunotek, through the trial monitor, will verify that:

- The source documents and other trial records are accurate, complete, updated, and correctly filed.

[name]  
Traductor-Intérprete Jurado de INGLÉS  
Nº 9971

- The data required by the protocol are accurately reported in the CRFs and are consistent with the source data.
- That both the principal investigator and the associate investigators follow the approved protocol and amendments, if any.
- That the written informed consent was obtained prior to each subject's participation in the trial.
- That the investigator and trial staff are performing the specified trial functions as set out in the protocol and have not delegated these functions to unauthorized individuals.
- That the investigator is only recruiting subjects who meet the selection criteria.
- That all doses and/or any treatment changes are well documented for each of the trial subjects.
- That the adverse events, concomitant treatments, and intercurrent illnesses are being reported in the CRFs in accordance with the provisions of the protocol.
- That the visits, tests, and examinations that the subjects failed to complete are clearly reported as such in the CRFs.
- That all withdrawals and dropouts of the subjects included in the trial are reported and justified in the CRFs.
- That all adverse events have been reported appropriately within the time frames established by the GCP guidelines, the protocol, the CREC, the sponsor, and the applicable legal regulations.
- That the investigator is retaining all essential documents.
- That the investigator has been informed of any deviation from the protocol, the Standard Operating Procedures, the Good Clinical Practices guidelines, and the

applicable regulations, and that the necessary measures have been applied to prevent recurrences of the deviations detected.

